## Covariates and Subgroups

The analysis of the efficacy endpoints may be adjusted by the following variables in the form of covariate analysis and/or subgroup analysis:

- UPCR <3.5 g protein/g creatinine versus UPCR  $\geq$ 3.5 g protein/g creatinine at baseline
- UPCR <1.5 g protein/g creatinine versus UPCR  $\geq$ 1.5 g protein/g creatinine at baseline
- Concomitant use of glucocorticoids and/or immunosuppressive medications (yes vs no)
- Concomitant use of Calcineurin Inhibitor (Cyclosporine, Tacrolimus) therapy (yes vs no)
  - a. Cyclosporin (yes vs.no)
  - b. All Calcineurin Inhibitors combined, i.e. Cyclosporin,or tacrolimus, etc. (yes vs.no)
- Concomitant use of ACE inhibitor or ARB or Aldosterone antagonist use vs not
- Concomitant use of use of diuretic/additional antihypertensive agent
  - a. Diuretics
  - b. Additional antihypertensive treatments
- Serum Albumin <3.5 g/dl vs  $\geq$ 3.5 g/dl at baseline
- Urinary albumin-to-creatinine ratio/Urinary protein-to-creatinine ratio  $\geq$ 1.5 vs < 1.5
- Patients with podocyte effacement of  $\geq$ 30% versus <30% based on electron microscopy
- Patients with glomeruli showing segmental lesions >1 vs  $\leq$ 1 based on electron microscopy

## 3.4 Efficacy Assessment

The overall efficacy hypothesis for this study is that CCX140-B will be effective in reduction in urine protein:creatinine ratio (UPCR) in treatment of subjects with FSGS. All available efficacy data will be listed for the ITT Population. Analyses of the efficacy endpoints will be performed using the ITT and PP populations, with the ITT population being the primary analysis population.

### 3.4.1 Primary Efficacy Endpoint

#### UPCR Change from Baseline

The primary efficacy endpoint (UPCR) will be summarized by treatment group over time using descriptive statistics. Spaghetti plots of UPCR as well as percent change of UPCR (derived from morning void spot urine. If missing 24 hour urine evaluations will be used, if available) from baseline to weeks 4, 8, 12, 13, 16, 20, 24, and week 28 (if available) will be produced by treatment group and for all individual patients for visual inspection. Additionally, percent change of UPCR from week 12 to week 13, 16, 20, 24, and week 28 will be summarized by prior treatment group during the open-label period. The same analyses of for UPCR will be performed at baseline, week 12 and week 24 solely using UPCR values derived from 24-hour urine evaluations (missing assessments will not be replaced with morning void spot urine values).

The primary analysis will use the morning void spot urine results. If baseline or post-baseline morning void spot urine results are not available, 24 hour urine results will be used where available. Please note 24-hour urine assessments at Day 1, Week 12 and Week 24 were added after Protocol Amendment 4.0.

For inferential analysis of the ratio to baseline, UPCR will be loge-transformed to alleviate skewness of the data since data are not normally distributed. A mixed effect model for repeated measures (MMRM) will be performed in the ITT population with treatment, group, visit, and treatment-by-visit interaction as factors and baseline value and age as covariates. Least squares mean differences and the corresponding 90% confidence intervals (CI) between each of the CCX140-B (5, 10, or 15 mg) groups and the placebo group will be back transformed to the original scale. Corresponding P-values will also be presented.

In the MMRM model, missing data will not be imputed. This analysis is unbiased under the missing at random (MAR) assumption. Toeplitz covariance matrix will be used to model within-subject variance-covariance structure for the model errors. If the model does not converge using the Toeplitz covariance matrix, AR(1) covariance matrix will be used. If convergence is still not met, then compound symmetry (CS) will be used.

The code used to generate the MMRM analysis will be similar to the following:

```
*****
Note:
TRT01AN = randomized treatment group (numeric):
    1=Placebo, 2=CCX140-B 5 mg, 3=CCX140-B 10 mg, 3=CCX140-B 15 mg
VISITN = Visit Number
LR2BASE = Ratio of Visit Value to Baseline Value (log-transformed)
LBASE = Baseline value of response (log transformed)
proc mixed data=lab_log;
  class SUBJID TRT01AN(ref='1') VISITN;
  model LR2BASE = TRT01AN LBASE AGE AVISITN TRT01AN*VISITN/ residual
    outp=residual ddfm=kr;
  Repeated VISITN / TYPE=TOEP sub=SUBJID;
  **use AR(1) if no convergence, then CS;
  lsmeans VISITN*TRT01AN / alpha=.10 cl pdiff slice=VISITN;
  ods output LSMeans=LSM
    Diffs=DiffLSM;
run;
*****
```

The same analysis described above will be performed for change from baseline in the open-label period and change from Week 12 in the open-label period.

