6.2. Randomization and Method of Treatment Assignment

Eligible subjects will be enrolled and stratified based on two stratification factors: UPCR <3.5 g protein/g creatinine at baseline versus UPCR ≥3.5 g protein/g creatinine at baseline, and on glucocorticoid/immunosuppressives or no glucocorticoid/ immunosuppressives, and randomized to one of the four treatment groups in a ratio of 1:1:1:1; placebo: 5 mg CCX140-B QD:10 mg CCX140-B BID: 15 mg CCX140-B BID. Randomization will be performed centrally via an interactive response technology (IRT) system and minimization algorithm, using the stratification factors. In order to protect the blinding, the randomization schedule will not be accessible to study personnel who have contact with study centers or who are involved in data management and analysis.

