### *2.2.2 Randomization and Blinding*

Randomization will be stratified by UPCR  $<3.5$  g protein/g creatinine versus UPCR  $\geq 3.5$  g protein/g creatinine at baseline and by the current use of glucocorticoids and/or immunosuppressive medications (yes vs no).

Blinded study medication will be taken by the subjects for 84 days, as follows:

- Group A: Three placebo tablets, taken twice daily;
- Group B: One 5 mg CCX140-B tablet and two placebo tablets in the morning; three placebo tablets in the evening;
- Group C: Two 5 mg CCX140-B tablets and one placebo tablet, taken twice daily;
- Group D: Three 5 mg CCX140-B tablets, taken twice daily.

Following the 84-day blinded dosing period, all subjects will take open label CCX140-B for an additional 84 days at the highest dose under evaluation, currently planned to be 15 mg twice daily.

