## Responder Analyses

The response rate across dose groups for patients achieving 30% reduction in UPCR (whenever available 24-hour urine evaluations will be used) from baseline at Week 12 will be calculated, with the number of subjects in the respective treatment group in the ITT (or PP) population being the denominator. The 90% Clopper-Pearson exact CIs will be estimated for the response rates in each treatment group. The estimated difference and its associated 90% CIs of response rates between each of the CCX140-B (5, 10, or 15 mg) groups and the placebo group will be provided using stratified analysis using the Newcombe hybrid-score method. The Stratification factors are the same as used in the randomization: UPCR  $<3.5$  g protein/g creatinine versus UPCR  $\geq 3.5$  g protein/g creatinine at baseline and by the current use of glucocorticoids and/or immunosuppressive medications (yes vs no) if there are enough responders. If there are not enough patients in any strata, the stratification variable will be removed from the model.

Non-responder imputation for non-allowed medications:

All subjects who started new therapy or increased the doses of an existing therapy that is clinically significant and was not allowed per protocol will be imputed as non-responders for the responder analysis. For example, the new use or clinically significant increase doses of an angiotensin converting enzyme (ACE) inhibitor, angiotensin receptor blocker (ARB) or other blocker of the renin angiotensin aldosterone system (RAAS) or new use of glucocorticoids, a calcineurin inhibitor or other immunomodulatory or immunosuppressive therapy will be reviewed before database lock.

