#### *3.4.2 Secondary Efficacy Endpoints*

Secondary efficacy endpoints include eGFR calculated by CKD-EPI cystatin C equation, CKD-EPI Creatinine equation, CKD-EPI Creatinine-Cystatin C equation and MDRD Creatinine equation. They will be summarized by treatment group over time using descriptive statistics. The analysis of these endpoints may be performed using a mixed-effects model for repeated measures (MMRM) with treatment group, visit, and treatment-by-visit interaction as factors, and baseline value and age as covariates. Point estimates, standard errors, the corresponding 90% confidence intervals and p-values for the differences between treatment groups will be displayed. The treatment comparisons of most interest will be the Least squares (LS) means contrasts of treatment difference at Week 12 and Week 24. In the MMRM model, missing data will not be imputed. For sensitivity analysis, the change in eGFR from baseline may also be analyzed using an analysis of covariance (ANCOVA) model, including treatment group as a factor and baseline value and age

as covariates. Missing data will be imputed by the last observation carried forward (LOCF) method. LS means, standard errors, 90% confidence intervals and p-values for the differences between treatment groups will be displayed. Secondary efficacy endpoints also include the proportion of subjects achieving complete/partial renal remission at Weeks 12 and 24 as defined in section 2.3.2. The proportion will be calculated using the number of subjects in the respective treatment group in the ITT (or PP) population as the denominator. The 90% Clopper-Pearson exact CIs will be estimated for the proportion in each treatment group. The between group comparison will also be carried out using the Newcombe hybrid-score method with a two-sided significance level of 0.10.

Stratified analyses will be conducted for testing difference in proportions between groups. The stratification variables are defined below as used in the randomization stratification. The stratification factor values as collected in the electronic case report forms (eCRFs) will be used for all stratified efficacy analyses, subgroup analyses and summaries of baseline characteristics.

- UPCR <3.5 g protein/g creatinine at baseline versus UPCR  $\geq$ 3.5 g protein/g creatinine at baseline;
- Current use of glucocorticoids/immunosuppressive medications (yes vs. no).

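### The primary UPCR MMRM has no committed term for the glucocorticoid/immunosuppressant allocation factor, and no spot-urine sensitivity model in the SAP relaxes its single-variance covariance

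*SAP*

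**What the plan says.** Protocol 6.2 states: "Randomization will be performed centrally via an interactive response technology (IRT) system and minimization algorithm, using the stratification factors". SAP 2.2.2 names the two factors: UPCR below versus at or above 3.5 g/g, and current use of glucocorticoids and/or immunosuppressants.

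The primary analysis in SAP 3.4.1 is an MMRM of log UPCR ratio to baseline, "with treatment, group, visit, and treatment-by-visit interaction as factors and baseline value and age as covariates". The model statement in the SAS code matches and has no glucocorticoid/immunosuppressant term. On covariance, "Toeplitz covariance matrix will be used to model within-subject variance-covariance structure for the model errors", coded as "Repeated VISITN / TYPE=TOEP sub=SUBJID", with AR(1) and then compound symmetry if the model does not converge.

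Elsewhere the SAP does commit to the allocation factors. For the UPCR responder analysis, "The Stratification factors are the same as used in the randomization"; for remission (SAP 3.4.2), "Stratified analyses will be conducted for testing difference in proportions between groups". Both allow a factor to be dropped if strata are too small. For efficacy endpoints generally, SAP Covariates and Subgroups and Protocol 9.3.9 make adjustment optional.

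The three sensitivity analyses in SAP 3.4.1 change the baseline definition, the urine source, or the data after non-allowed medication. Protocol 9.3.5 commits to ANCOVA with LOCF as a sensitivity analysis alongside the UPCR MMRM. SAP 3.4.2 carries ANCOVA forward for eGFR only, as an option. SAP section 6 lists two additions and no removals.

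**The concern.** With about 10 subjects per arm, the Week 12 dose-versus-placebo ratios and their 90% CIs are the main efficacy output, so the width of those intervals matters.

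First, the UPCR stratum is largely captured by continuous log baseline UPCR, but nothing in the model captures glucocorticoid/immunosuppressant use. Balancing arms on a prognostic factor and then leaving it out of the model leaves its variance in the residual, so the interval is wider than it need be. The responder and remission analyses use the factor while the primary one does not.

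Second, under TOEP, AR(1) or CS the Week 12 standard error uses a variance pooled over all modelled visits. If the true Week 12 variance differs from that pooled value, the interval has the wrong width. The protocol's ANCOVA uses a single-timepoint variance and would have given an alternative interval. It is absent from the SAP for UPCR without being declared.

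**Working it through.** **Plan's own figure.** Inputs: SD 0.70, 10 per arm, two-sided alpha 0.10 (Protocol 9.4; SAP 2.2.4 and 3.1.5). Half-width = t(0.95, 18) × 0.70 × √(2/10) = 1.734 × 0.70 × 0.4472 = 0.543. For a ratio of 0.5, exp(ln 0.5 ± 0.543) gives 0.29 to 0.86. Both stated figures reproduce.

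**Part 1: the omitted factor.** The documents give neither the factor's effect nor its prevalence, so both are assumed. For effect g on the log scale and prevalence p, the share of variance explained is R² = g²·p(1−p)/0.70². The unadjusted interval is wider by 1/√(1−R²) − 1, before the one-degree-of-freedom cost. At p = 0.5:

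| g | R² | Unadjusted CI wider by |
|---|---|---|
| 0.2 | 0.01/0.49 = 2.0% | 1.0% |
| 0.3 | 0.0225/0.49 = 4.6% | 2.4% |
| 0.4 | 0.04/0.49 = 8.2% | 4.3% |
| 0.6 | 0.09/0.49 = 18.4% | 10.7% |

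A null simulation checked this: 2,000 replicates per scenario, 40 subjects minimised to four arms, 15% dropout completely at random, Toeplitz REML with Kenward-Roger, visits at Weeks 1, 2, 4, 8 and 12. Adding the factor changed the Week 12 half-width by +0.3% (0.557 to 0.559) at g = 0, and by −0.8, −2.1, −4.0 and −9.5% at the four effects above. Break-even solves 0.0027 = 0.5·g²·0.25/0.49, so g ≈ 0.10, a ratio of about 1.1. Without the factor, coverage ran from 90.1% (g = 0) to 93.0% (g = 0.6): valid, and conservative where the factor matters.

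**Part 2: the single variance.** The documents give one SD and none by visit, so the visit patterns are assumed, with Week 12 fixed at 0.70. Approximate coverage = 2·F(1.691 × pooled SD/0.70) − 1, where F is the t distribution on 34 df (40 subjects less four arms, baseline and age), pooled SD is the root mean square over modelled visits, and there is no dropout. For example, for the larger rise over five visits: pooled SD = √[(0.50² + 0.53² + 0.58² + 0.65² + 0.70²)/5] = 0.597; 1.691 × 0.597/0.70 = 1.441; coverage 84.1%.

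| SD at Weeks 1/2/4/8/12 | All five visits | Weeks 4, 8, 12 only |
|---|---|---|
| Constant 0.70 | 90.0% | 90.0% |
| 0.60/0.61/0.63/0.67/0.70 | 87.0% | 88.4% |
| 0.50/0.53/0.58/0.65/0.70 | 84.1% | 87.2% |
| 0.80/0.79/0.77/0.73/0.70 | 92.4% | 91.5% |

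The second column matters because SAP 3.4.1 does not list the visits that enter the MMRM. Weeks 1 and 2 are collected and have analysis windows, but the plots in that section start at Week 4.

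Simulated five-visit Toeplitz coverage was 90.2, 87.3, 84.4 and 92.8% in the same order. An unstructured covariance covered 90.3 to 90.5% and a Week 12 observed-case ANCOVA 90.1%.

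**24-hour-only analysis.** Week 12 is its only double-blind post-baseline visit, so it avoids the pooling. It covers only subjects with collections, which the SAP says were not available for all. With half-width t(0.95, n−6) × 0.70 × √(2/(n/4)), n = 40, 30 and 20 give 0.53, 0.62 and 0.78.

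**The case against.** The case for leaving the plan alone has substance.

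- Adjustment is already permitted. The outcome is change from baseline with log baseline in the model, and background doses must be stable for four weeks before screening and projected stable through Week 12. A large residual effect cannot be presumed, and no document supports 0.6 log units. This stands: the likely gain is small. So is the cost.
- The optional list in SAP Covariates and Subgroups refers to concomitant use, which SAP 3.3.6 defines to include drugs first taken after dosing starts. A reader might infer that any adjustment would use the wrong variable. SAP 3.4.2 weakens that inference: it fixes the eCRF stratification values for all stratified and subgroup analyses. The wording is loose, but the allocation factor is identified and collected.
- A reader might infer that unequal variances would go unseen. That is too strong. UPCR is to be summarised by arm over time with SDs (SAP 3.4.1 and 3.1.4), individual profiles are plotted, and the code outputs residuals. These are indirect checks, and the SDs may be on the raw scale. None supplies an alternative interval.
- MCP-Mod gives 90% CIs for the primary endpoint, but the SAP does not state its variance model or whether its inputs are raw values or MMRM estimates. It cannot be counted as a check.
- A parsimonious covariance is defensible at this sample size, and the protocol itself cautions that inferential analysis may not be appropriate. This stands, and it is why TOEP can remain primary.
- The missing ANCOVA is mainly a documentation gap, since the SAP supersedes the protocol. Section 6 is still incomplete on this point.

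**Conclusion.** Both parts hold, at minor severity.

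The primary double-blind MMRM lacks a committed term for an allocation factor that other planned analyses use. The cost is precision. Inferring bias or an invalid interval would go too far: simulated coverage without the term was at or above nominal. The size depends on an assumed effect and prevalence.

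No spot-urine UPCR sensitivity model listed in the SAP relaxes the common variance, and a protocol-committed analysis that would have done so was dropped without being declared. It would be tempting to conclude that the Week 12 intervals will be too narrow. The documents do not support that: they give no visit-specific SDs, and the assumed patterns include one with no error and one that is conservative. The worst shortfall shown is about 6 percentage points with five visits and about 3 with three.

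The study is exploratory, at alpha 0.10 without multiplicity adjustment. What is affected is the precision and reading of the dose estimates, not a confirmatory decision.

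**What to change.** 1. Add glucocorticoid/immunosuppressant use at randomisation (yes/no, the eCRF stratification value) as a fixed effect in the primary double-blind UPCR MMRM, in text and code. Cost: one model term, one degree of freedom, and about 0.3% in half-width if the factor has no effect. No new data are needed.
2. Keep TOEP as primary and add one spot-urine UPCR sensitivity analysis: either the same MMRM with visit-specific variances (UN, then TOEPH, then CSH on non-convergence, with ddfm=kr), or a Week 12 ANCOVA. Cost: one extra model run. At five visits UN has 15 covariance parameters against 5 for TOEP, which is why it is proposed only as a sensitivity analysis; it converged in all 8,000 simulated data sets (four SD patterns × 2,000).
3. In SAP section 6, list any protocol analysis that is dropped, including the UPCR ANCOVA/LOCF if its removal is intended. Cost: one line.

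### The SAP's sample code for the primary UPCR model gives two dose arms the same treatment code and uses an undefined visit variable, contradicting the text it implements

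*SAP*

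**What the plan says.** SAP Section 3.4.1 (UPCR Change from Baseline) describes the primary model in prose: an MMRM on the log ratio to baseline "with treatment, group, visit, and treatment-by-visit interaction as factors and baseline value and age as covariates". The reported output is the set of least-squares mean differences and 90% intervals "between each of the CCX140-B (5, 10, or 15 mg) groups and the placebo group will be back transformed to the original scale". That is three dose contrasts at each visit, with visit as a categorical factor.

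The same section then gives sample code, introduced as resembling what will finally be run. Its note defines the treatment variable as "1=Placebo, 2=CCX140-B 5 mg, 3=CCX140-B 10 mg, 3=CCX140-B 15 mg" and the visit variable as "VISITN = Visit Number". The statements are:

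- CLASS: "class SUBJID TRT01AN(ref='1') VISITN"
- MODEL: "model LR2BASE = TRT01AN LBASE AGE AVISITN TRT01AN*VISITN/ residual"
- REPEATED: "Repeated VISITN / TYPE=TOEP sub=SUBJID"
- LSMEANS: "lsmeans VISITN*TRT01AN / alpha=.10 cl pdiff slice=VISITN"

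AVISITN appears only in MODEL. The note does not define it and CLASS does not list it.

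**The concern.** The block is the SAP's only code-level statement of the primary model, and it departs from the prose in two places.

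First, 10 mg and 15 mg twice daily share the value 3 and no level 4 exists. An analysis data set derived from that note would not separate the two higher regimens, in a trial designed to compare doses.

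Second, an unlisted variable in PROC MIXED is treated as continuous. As printed, visit enters as a straight line beside a full treatment-by-visit interaction, and the two are redundant with each other.

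The Week 12 contrasts of each regimen with placebo are the primary efficacy result. The same model is reused for the open-label, sensitivity, per-protocol and MCP-1-adjusted analyses of UPCR, so a slip carried into the program would spread. The SAP also supersedes the protocol's analysis section, so a conflict inside it should be settled there.

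**Working it through.** **Inputs.** Four arms of 10 (SAP 2.2.1). SD 0.70 for log UPCR change and 90% half-width 0.543 (protocol 9.4, SAP 2.2.4). Double-blind visits at Weeks 1, 2, 4, 8 and 12, target days 8, 15, 29, 57 and 85 (SAP Table 1). The code as printed. The check is algebraic, on the design matrix; the code was not executed in SAS.

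**1. The plan's own figure.** Half-width = t(0.95; 18) × SD × √(2/10) = 1.734 × 0.70 × 0.447 = 0.543. At a ratio of 0.5 the interval is 0.5 × exp(±0.543) = 0.29 to 0.86. Both match. This is the precision planned for one dose against placebo.

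**2. Arm codes 1, 2, 3, 3.** The treatment variable has three levels, with 10, 10 and 20 subjects. There are 3 − 1 = 2 placebo contrasts per visit instead of 4 − 1 = 3. The pooled contrast has simple half-width t(0.95; 28) × 0.70 × √(1/20 + 1/10) = 1.701 × 0.70 × 0.387 = 0.461, so it looks tighter than the planned 0.543. As an illustration with assumed values, true ratios of 0.8 (10 mg) and 0.5 (15 mg) would appear as one ratio of about √(0.8 × 0.5) = 0.63.

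**3. AVISITN as printed, arms coded correctly.** Suppose AVISITN is numeric and takes one value v_j at visit j. Leaving out baseline and age, the mean for arm a at visit j is

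μ + τ_a + β·v_j + γ_aj.

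The column for v_j is a linear combination of the interaction columns, so β is not estimable. LSMEANS sets a continuous covariate at its overall mean v̄ and asks for μ + τ_a + β·v̄ + γ_aj. This differs from the cell mean by β(v̄ − v_j), so it is estimable only if v̄ = v_j. In the difference from placebo at the same visit the β·v̄ terms cancel, leaving (τ_a − τ_1) + (γ_aj − γ_1j), which is estimable.

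With complete data v̄ is (1+2+4+8+12)/5 = 5.4 in weeks, (8+15+29+57+85)/5 = 38.8 in days, and 3.0 for consecutive codes 1 to 5. Testing every vector against the row space, with baseline and age included, gives:

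| AVISITN coded as | v̄, complete data | Means estimable, complete | Means estimable, 10% missing | Differences estimable |
|---|---|---|---|---|
| Weeks | 5.4 | 0 of 20 | 0 of 20 | 15 of 15 |
| Days | 38.8 | 0 of 20 | 0 of 20 | 15 of 15 |
| Consecutive | 3.0 | 4 of 20 (Week 4 only) | 0 of 20 | 15 of 15 |

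Week 12 has the largest value among the double-blind visits, so it cannot equal the mean once any earlier visit is in the data. The only exception is a middle visit that happens to coincide with v̄. For instance, if only Weeks 4, 8 and 12 were modelled, v̄ = 24/3 = 8 and Week 8 would be estimable with complete data.

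**4. Both slips together.** For the double-blind visits with AVISITN in weeks or days, 0 of 15 means and 10 of 10 differences are estimable. For all ten post-baseline visits with complete data, the counts are 0 of 30 and 20 of 20.

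**5. Effect on the estimates.** In one simulated four-arm data set the three log-scale differences from placebo were −0.1917, −0.1293 and −0.7947 under the intended model, and the same under the model with AVISITN continuous. With merged codes the last two were replaced by a single −0.4653.

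**6. After correction.** With codes 1 to 4 and VISITN as the class main effect, 20 of 20 means and 15 of 15 differences are estimable.

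**The case against.** The strongest reply is that these are typing slips in an illustration. The duplicate 3 is in a descriptive note; no executable line assigns treatment codes, so PROC MIXED uses whatever the data set holds. The prose is clear on three doses and on visit as a factor, the protocol (9.3.5) agrees, and the SAP's dose-response section gives placebo and the three doses four distinct levels. Detailed programming specifications are a separate document (SAP Section 7). The visit slip leaves the inferential output, the differences from placebo, untouched. Three treatment levels in a four-arm trial, or means flagged as non-estimable, would probably be noticed on first run.

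Most of this stands, and it rules out two stronger readings. A reader might infer that running the block merges two arms. It does so only if the treatment variable is derived as the note says. A reader might also infer that the AVISITN slip destroys the primary comparison. It does not, because the same-visit differences survive. The non-estimability result is itself conditional. If AVISITN is absent there is no fit and so no wrong answer. SAP 3.1.2 maps unscheduled and early-termination records to analysis visits; if that gave several AVISITN values under one VISITN, the redundancy could break and the means could become estimable, though with an unintended linear visit term in the model.

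The reply does not remove the contradiction. The note and the MODEL statement disagree with the text they implement, and the code explicitly exports the least-squares means as well as the differences. A merged result might also be less conspicuous than it seems: the SAP separately allows the 10 mg and 15 mg twice-daily groups to be pooled if responses are similar, and its dose-response scale uses 3 for 15 mg alone.

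**Conclusion.** The point holds as a specification error in the sample code for the primary analysis. The duplicate treatment code is the more serious half: followed literally, it removes the separate 10 mg and 15 mg twice-daily estimates and gives two placebo contrasts where three are promised. The undefined visit variable either stops the step or, if numeric and constant within visit, makes the arm-by-visit means non-estimable. That is 0 of 20 in general, with only a coincident middle visit escaping and never Week 12 in the double-blind model. All 15 differences from placebo are unaffected by it.

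The documents do not support the conclusion that the primary result will be wrong. The code is expressly approximate, the intent is plain from the prose, and either fault would probably surface when the program is run or checked. The size of the problem is a conflict to remove before programming.

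**What to change.** Make two edits to the code block in SAP Section 3.4.1.

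1. In the note, define TRT01AN as 1 for placebo, 2 for 5 mg once daily, 3 for 10 mg twice daily and 4 for 15 mg twice daily.
2. Use one visit variable in CLASS, MODEL, REPEATED and LSMEANS by replacing AVISITN with VISITN in MODEL. It would help to say in the note whether VISITN carries the analysis visit assigned under Section 3.1.2.

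Neither edit changes the design, the data collected or the intended analysis. The cost is two corrections to SAP text, plus a check that the programming specifications and any code already written use the corrected definitions.
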